### 3.2.5 Monthly time intervals

A month is defined as 30 days and time intervals based on monthly durations are defined as a multiple of 30 days (eg, 12 months is defined as 360 days). The following definitions of 3-month and 6-month intervals are based on 30-day months where the date of first dose of BRV is Day 1:

| Interval | Duration Definition |
|-----------------|----------------------------|
| Months 1-3      | Days 1-90                  |
| Months 4-6      | Days 91-180                |
| Months 7-9      | Days 181-270               |
| Months 10-12    | Days 271-360               |
| Months 1-6      | Days 1-180                 |
| Months 7-12     | Days 181-360               |
| Months 13-18    | Days 361-540               |
| Months 19-24    | Days 541-720               |

Subsequent 3- and 6-month intervals are defined in a similar manner.

Six-month intervals are defined for the evaluation of direct and indirect cost parameters. Statistical summaries for direct and indirect cost parameters will only present results through the first 2 years of treatment. Three-month intervals will be used for analysis of efficacy outcomes and AEs.

End date is the date of last dose of BRV.

For the analysis of efficacy outcomes, a subject is included in the analysis for a 3-month interval if the end date is on or after the *last day* of the 3-month interval and the subject diary was completed for at least 1 day during the 3-month interval.

For the analysis of AEs, a subject is included in the analysis for a 3-month interval if the end date is on or after the *first day* of the 3-month interval.

### 3.2.6 Last value on BRV treatment

Last Value for QOLIE-31-P, HADS, EQ-5D, and socio-professional data is the last assessment strictly after the date of first dose of BRV and up to and including the YEV at the end of the second year and any EDVs for subjects who did not complete through the YEV at the end of the second year.

Last Value for clinical laboratory parameters, vital signs, and ECGs is the last available result obtained after the first dose of BRV and prior to or on the date of last dose of BRV. All scheduled and unscheduled assessments within this time period will be considered. Last Value will be determined separately for each laboratory parameter for hematology, chemistry, and urinalysis assessments.

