13.1.2.2 Other Safety Variables

- Laboratory tests (blood chemistry, hematology, and urinalysis)
- Vital signs (SBP, DBP, pulse rate) and body weight
- Electrocardiogram
- Physical and neurological examination
- Change in HADS scores from the Baseline of the previous study to each assessment for the first 2 years and to the last Evaluation Period assessment during the first 2 years

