## 2.3 Study Design and Conduct

This is an open-label, long-term follow-up, multicenter, multinational, noncomparative, single-arm study of BRV. The primary objective is to evaluate the long-term safety and tolerability of BRV at individualized doses up to a maximum of 200mg/day in subjects suffering from epilepsy. The secondary objective is to evaluate the maintenance of efficacy over time of BRV. Exploratory objectives are to assess the effects of BRV on subjects' Health-Related Quality of Life (HRQoL), obtain information on the direct and indirect costs and subjects' self-reported health status.

At the time of development of this SAP, the enrollment into N01315 had completed. Study N01315 enrolled subjects 16 years of age and older who had completed N01276 or N01306.

Subjects who enrolled in the study entered an Evaluation Period at a recommended starting dose of 100mg/day. The dose of BRV could then be adjusted based on the individual subject's seizure control and tolerability. Dose increases could be made in increments of a maximum 50mg/day on a weekly basis and up to a maximum dose of 200mg/day; dose decreases could be made in steps of maximum 50mg/day on a weekly basis with a last down-

titration step at 20mg/day for 1 week. Subjects who completed the Down-Titration Period or subjects who discontinued during the Evaluation Period without entering the Down-Titration Period enter a Study Drug-Free Period for a minimum of 2 weeks and a maximum of 4 weeks. The maximum allowable daily dose for this study was increased from 150mg/day to 200mg/day based on integrated amendment 2 to the protocol. The daily dose should have been administered in 2 equal intakes (morning and evening), taken with or without food.

Subjects entering N01315 on BRV monotherapy could have converted to adjunctive BRV treatment during the N01315 study. In this case, as well as for subjects entering N01315 taking BRV and a concomitant AED, the Investigator may have adapted the concomitant AED drug/dosage for safety or efficacy reasons. In case of excellent efficacy and tolerability of BRV, withdrawal of concomitant AED(s) resulting in monotherapy with BRV may have been re-attempted by the Investigator.

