### 3.2.4 Study periods

The study is divided into 3 periods: Evaluation Period, Down-Titration Period, and Post-Treatment Period. A subject is classified as “discontinued” if the subject has a termination case report form (CRF) or has an early discontinuation visit (EDV). A subject is classified as “completed” if this subject completes the full extent of the study as defined in the protocol at database lock.

A “discontinued” subject can be potentially slotted into the 3 periods of the study. The following algorithms will be used to slot the subject appropriately into the Evaluation Period, Down-Titration Period, and Post-Treatment Period.

- For Evaluation Period, the start date is the date of first dose of BRV, and the following algorithm is used to determine the end date:
  - If the subject enters the Down-Titration Period, then the date of EDV is the end date;
  - If the subject does not enter the Down-Titration Period but meets 1 of the following criteria, the Evaluation Period ends on date of last dose of BRV:
    - Without an EDV but having a termination CRF,
    - With an EDV and having a termination CRF,
    - With an EDV and the date of EDV prior to the database lock date and having no termination CRF.
- A subject is considered entering Down-Titration Period only if the subject has an EDV and at least 1 dose of study drug after the date of EDV, the start date of Down-Titration Period is set as 1 day after the date of EDV, and the Down-Titration Period ends on date of last dose of BRV. A subject without an EDV but having a termination CRF or with an EDV but without any dosing of study drug after the EDV will not have the Down-Titration Period, and no artificial Down-Titration Period will be created for analysis.
- A subject is considered entering the Post-Treatment Period if the subject has at least 1 contact (scheduled visit, unscheduled visit, or telephone contact) after the date of last dose of BRV. The Post-Treatment Period starts 1 day after date of last dose of BRV irrespective of entering the Down-Titration Period, and there is no end date.

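### SAP 3.2.6 lets an EDV held after the last dose supply the on-treatment Last Value for QOLIE-31-P, HADS and EQ-5D, which does not fit the SAP's own study periods

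*SAP*

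**What the plan says.** SAP 3.2.6 has two rules under one heading, *Last value on BRV treatment*.

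- Questionnaires: "Last Value for QOLIE-31-P, HADS, EQ-5D, and socio-professional data is the last assessment strictly after the date of first dose of BRV". The upper limit is set by visit: "up to and including the YEV at the end of the second year and any EDVs for subjects who did not complete" through the Month 24 visit. The date of last dose is not mentioned.
- Laboratory parameters, vital signs and ECGs: the last result "obtained after the first dose of BRV and prior to or on the date of last dose of BRV".

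SAP 3.2.4 sets the periods for discontinued subjects. With down-titration, the Evaluation Period ends on the EDV date. Without it, "the Evaluation Period ends on date of last dose of BRV", and one of the listed cases is "With an EDV and having a termination CRF". The Post-Treatment Period starts the day after the last dose.

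Protocol 13.1.2.2 defines the HADS variable as change from Baseline to each assessment in the first 2 years and "to the last Evaluation Period assessment during the first 2 years". Protocol 13.1.2.4 does the same for QOLIE-31-P, and for EQ-5D it names the last assessment in the first 2 years of the Evaluation Period. SAP 2.2 repeats these variables.

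SAP 8.2.4, 8.2.5 and 11.4.6 use Last Value for the Efficacy Analysis Set (QOLIE-31-P, EQ-5D) and the Safety Analysis Set (HADS). None of them adds a last-dose limit, except that the QOLIE-31-P prioritization rankings are tied to the first 2 years of the Evaluation Period.

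**The concern.** A table row labelled as the last value on treatment should hold on-treatment scores. If a subject stops BRV, does not down-titrate and attends the EDV some days later, the questionnaire rule still selects that EDV. The score then describes the subject after stopping: it may show recovery, withdrawal effects or no change. For the same visit, the laboratory, vital-sign and ECG results would be left out of Last Value.

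Last Value deserves care because the visit cohorts in SAP 3.2.8 start at Month 6, so someone who leaves before then is in no cohort. Last Value is the one summary that takes a single end-of-treatment score from each subject whenever they left. HADS is also one of the listed safety variables.

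**Working it through.** The documents state no figure on this point, so the main check compares the rules case by case.

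**1. Where does the EDV fall, and is it selected?** These cases apply to a subject who leaves before the Month 24 visit.

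| Case | Evaluation Period ends (SAP 3.2.4) | EDV falls in | EDV is Last Value under 3.2.6 | Consistent? |
|---|---|---|---|---|
| EDV, then down-titration | EDV date | Evaluation Period | Yes | Yes |
| EDV on the day of last dose, no down-titration | Last-dose date | Evaluation Period | Yes | Yes |
| Transfer to another BRV study or access program, still on BRV at the EDV | EDV not after last dose | Evaluation Period | Yes | Yes |
| Last dose, no down-titration, EDV on a later day | Last-dose date | Post-Treatment Period | Yes | **No** |

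Only the fourth case is affected. SAP 3.2.4 allows for it, because its last-dose rule covers subjects who have an EDV and do not down-titrate. It does not say how often the case arises.

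**2. Is such an EDV off drug?** Protocol 6.2 gives a plasma half-life of about 8 hours in young healthy men. The fraction remaining after t hours is 2^(−t/8).

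- 24 h: 2^(−3) = 12.5%
- 48 h: 2^(−6) = 1.6%

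On that half-life, an EDV two or more days after the last dose is effectively off drug. Half-life in this population may differ.

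**3. How far could the mean move?** Shift in mean Last Value = f × d, where f is the share of subjects whose Last Value is an off-drug EDV and d is the change in score from on to off drug. Neither is in the documents. The values below are assumptions for illustration, applied to the 108 enrolled subjects in SAP 2.4; the actual denominator is the number with a Last Value.

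- f = 0: no shift.
- f = 5% (0.05 × 108 = about 5 subjects), d = 1 HADS point: 0.05 × 1 = 0.05 points.
- f = 20% (0.20 × 108 = about 22 subjects), d = 3 HADS points: 0.20 × 3 = 0.6 points.

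So the range is 0 to 0.6 points on the 0–21 scale, in either direction.

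**4. What would a last-dose limit remove?** In this study the questionnaires are scheduled at Months 2, 6, 12, 18 and 24 and at the EDV; Protocol Table 5:1 has none at the Entry Visit. A subject who stops before Month 2 and has a later EDV would have no on-treatment value. For later stoppers the widest gap between scheduled assessments is 12 − 6 = 6 months, so with no missed visit the fallback score is up to about 6 months old.

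**The case against.** The strongest reply is that the EDV score is worth keeping. Protocol 11.1.20 asks for the questionnaires at any EDV in the first 2 years, whether or not the subject is still taking drug. Dropping that score replaces it with an older one, perhaps from before the problem that led to stopping, or with nothing. This stands. It is the reason to show both versions rather than simply discard the late EDV.

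It is also fair that the planned order is EDV first and down-titration after (Protocol 11.1.24), so an EDV held as planned is on drug. HADS change is also summarized by visit (SAP 11.4.6), TEAEs leading to permanent discontinuation have their own table (SAP 11.2.2), and abnormal psychiatric findings are listed (SAP 11.4.5). Mood worsening on BRV would not be visible only through Last Value. These points reduce the weight of the problem but do not reconcile SAP 3.2.6 with SAP 3.2.4.

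A reader might infer three stronger things that the documents do not support.

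- **A departure from the protocol that SAP 2.5 should have declared.** Protocol 13.1.3 runs the Evaluation Period from Visit 1 to the last Evaluation Visit and does not say whether an EDV counts as one. The last-dose cut-off comes only from the SAP.
- **An off-drug EDV as the expected pattern.** SAP 2.3 mentions "subjects who discontinued during the Evaluation Period without entering the Down-Titration Period", and SAP 3.2.4 says a subject "with an EDV but without any dosing of study drug after the EDV will not have the Down-Titration Period". Neither places the EDV after the last dose.
- **Last Value hides on-treatment worsening because abrupt stoppers are mainly tolerability cases.** Neither document gives reasons for abrupt stopping, and withdrawal effects could push the scores the other way.

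**Conclusion.** The point holds as an inconsistency inside the SAP. For QOLIE-31-P, HADS and EQ-5D, SAP 3.2.6 can select a score that SAP 3.2.4 places in the Post-Treatment Period. That score does not match the section's heading or the variables in SAP 2.2, and it is handled differently from laboratory, vital-sign and ECG data in the same section.

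The point is minor. It touches only subjects whose EDV came after their last dose and who left before the Month 24 visit; their number is unknown and may be zero. The 0 to 0.6 point HADS range is arithmetic on assumed inputs, not an estimate, and the direction is open. The outcomes are not primary, all summaries are descriptive, and no test or error rate is involved.

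**What to change.** In SAP 3.2.6, define Last Value for QOLIE-31-P, HADS and EQ-5D as the last assessment after the first dose and on or before the end of the SAP 3.2.4 Evaluation Period, within the first 2 years. SAP 3.2.4 spells out that end date only for discontinued subjects; where it gives none, the last-dose limit already used for laboratory data can serve. EDVs that precede down-titration or fall on the last-dose day stay in.

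Report EDV scores obtained after the last dose in a separate row, and repeat the Last Value summary with them included as a sensitivity display. Socio-professional data need no change, since SAP 8.2.8 only lists them.

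The cost is one sentence in the SAP, one extra row and one repeated display per questionnaire, with no new data collection. The real downside is the loss shown in step 4 of the working: no on-treatment Last Value for some subjects who stop before Month 2, and an older score for some who stop later. The sensitivity display lets a reader see whether that matters.

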### 3.2.7 Exposure duration and exposure duration cohorts

At the final analysis, the overall duration of exposure (or On Treatment Period) will be calculated as the date of last dose of BRV minus the date of first dose of BRV plus 1 day.

Each subject will be classified into one or more of the following exposure duration cohorts based on the duration of BRV exposure as calculated above:

|              |           |
|--------------|-----------|
| All subjects | ≥1 day    |
| ≥3 months    | ≥90 days  |
| ≥6 months    | ≥180 days |
| ≥12 months   | ≥360 days |

This categorization will continue in 6-month increments past 12 months up to a time point that will be determined based on cumulative exposure at the time of the database lock.

### **3.2.8 Study visit cohorts**

Study visit cohorts are defined for summaries of QOLIE-31-P, HADS, and EQ-5D. Six-month, 12-month, 18-month, and 24-month cohorts are defined. Subjects will be classified into a study visit cohort if they attend the scheduled visit at the time point defined by the cohort. For example, subjects will be included in the 18-month study visit cohort if they attend the scheduled visit at 18 months (ie, FEV at Month 18). Subjects may be classified in more than 1 cohort. Generally, subjects included in a cohort for a later visit will be included in all earlier study visit cohorts (eg, 6-month and 12-month study visit cohorts for subjects in the 18-month study visit cohort), although this may not be the case in the event of a missed visit or if an unscheduled visit is conducted in lieu of a scheduled visit.

### **3.3 Definition of Baseline Values**

Baseline for all study outcomes will be based on baseline from the previous studies. For assessments performed at scheduled and unscheduled visits, Baseline will generally be the last result obtained or prior to the randomization visit of the previous study. Baseline will be defined separately for each hematology, blood chemistry, and urinalysis parameter.

Baseline for the evaluation of seizure frequency and seizure days will be calculated from the core study seizure diary based on the rules defined in Section 3.8.1.

### **3.4 Protocol deviations**

The criteria for identifying important protocol deviations and the classification of important protocol deviations will be defined separately in the Specification of Protocol Deviations document. Whenever possible, criteria for identifying important protocol deviations will be implemented algorithmically to ensure consistency in the classification of important protocol deviations across all subjects.

### **3.5 Analysis Sets**

#### **3.5.1 Safety Analysis Set**

The Safety Analysis Set will consist of all subjects who took at least 1 dose of study drug.

Summaries of demographics and baseline characteristics, medical history, AEDs, non-AEDs, HADS, direct and indirect cost parameters, socio-professional data, study drug exposure, and safety outcomes will be provided for the Safety Analysis Set.

### **3.5.2 Efficacy Analysis Set**

Efficacy Analysis Set will consist of all subjects who took at least 1 dose of study drug and have at least 1 seizure diary day during the Evaluation Period.

Summaries of seizure outcomes, epilepsy history, QOLIE-31-P, and EQ-5D will be provided for the Efficacy Analysis Set.

### **3.6 Treatment Assignment and Treatment Groups**

This is an uncontrolled study in which all subjects receive BRV in doses that are optimally adjusted for each subject. Generally, statistical summaries will present all subjects combined as a single treatment arm unless otherwise indicated.

### **3.7 Coding dictionaries**

Medical history, AEs, and concurrent medical procedures will be coded using the Medical Dictionary for Regulatory Activities (MedDRA). Medications will be coded using the World Health Organization Drug Reference List (WHO-DRL). Prior medical procedures will not be coded.

### **3.8 Definitions of Study-specific Derived Variables**

#### **3.8.1 Calculation of seizure frequency/days**

##### **3.8.1.1 Initial seizure data processing**

Each seizure code in the clinical database will be mapped to exactly 1 of the following codes based on the 1981 International League Against Epilepsy (ILAE) classification: I, IA, IA1, IA2, IA3, IA4, IB, IB1, IB2, IC, II, IIA, IIB, IIC, IID, IIE, IIF, or III.

Seizures reported as “too frequent to count” will not have a reported frequency; the count of 1 will be used for analyses.

##### **3.8.1.2 Calculation of adjusted seizure frequency**

Baseline POS frequency for seizure types I, IA, IB, IC, and for all seizure types (I+II+III) will be obtained from the Baseline Period of the previous study.

The total number of seizures for seizure types I, IA, IB, and IC, and the total number of seizures for all seizure types (I+II+III) will be calculated overall, by 3-month time intervals, and over the cohort interval for each exposure duration cohort. All seizure diary on or after the date of first dose of BRV and prior to or on the date of last dose of BRV will be considered for these calculations.

Twenty-eight day adjusted seizure frequency for seizure types I, IA, IB, and IC, and for all seizure types (I+II+III) will be calculated overall, within each 3-month time interval, and over each exposure duration cohort interval by dividing the total number of seizures for each seizure type by the number of days for which the diary was completed overall, within each 3-month interval, and within each exposure duration cohort interval, and multiplying the resulting value by 28.

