13.1.2.4 Other Efficacy Variables

- Partial onset seizure (type I) frequency per 28 days during the Evaluation Period

- Percent reduction in POS (type I) frequency per 28 days from Baseline of the previous study to the Evaluation Period
- Percentage of subjects continuously seizure-free for all seizure types (I+II+III) for at least 6 months and at least 12 months during the Evaluation Period
- Change in QOLIE-31-P scores from Baseline of the previous study to each assessment for the first 2 years and to the last Evaluation Period assessment during the first 2 years
- EuroQoL-5 Dimensions questionnaire response for each assessment for the first 2 years for the Evaluation Period and for the last assessment during the first 2 years of the Evaluation Period

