13.1.3.2.2 Other Efficacy Analyses

The percentage reduction in 28-day POS frequency relative to Baseline will be summarized using descriptive statistics. Baseline will be defined as the Baseline value from the previous study. Additionally, the number and percentage of subjects continuously seizure-free during the Evaluation Period will be presented. Descriptive statistics for the change in QOLIE-31-P and EQ-5D from Baseline of the previous study to each visit during the first 2 years of the study and the last Evaluation Period Visit will also be presented.

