### 2.2.2.2 Other efficacy variables

- Partial onset seizure (POS) (type I) frequency per 28 days during the Evaluation Period
- Percent reduction in POS (type I) frequency per 28 days from Baseline of the previous study to the Evaluation Period
- Percentage of subjects continuously seizure-free for all seizure types (I+II+III) for at least 6 months and at least 12 months during the Evaluation Period
- Change in Patient Weighted Quality of Life in Epilepsy Questionnaire (QOLIE-31-P) scores from Baseline of the previous study to each assessment for the first 2 years and to the last Evaluation Period assessment during the first 2 years
- EuroQol-5 Dimensions (EQ-5D) questionnaire response for each assessment for the first 2 years for the Evaluation Period and for the last assessment during the first 2 years of the Evaluation Period

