A “completed” subject can potentially have Evaluation Period, Down-Titration Period, or Post-Treatment Period. At the time of study termination by the Sponsor, subjects will discontinue the study drug following the down titration process or will be converted without titration to commercial BRV where available; alternatively, subjects may be initiated without down-titration in a managed access program, named patient program, compassionate use program, or similar type of access program as allowed per country specific requirements in addition to legal and regulatory guidelines.

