### 8.2 Analyses of Other Efficacy Variables

#### 8.2.1 Partial onset seizure frequency

Twenty-eight day adjusted POS frequency will be summarized with quantitative descriptive statistics for all subjects for the Baseline Period, the On Treatment Period, and by 3-month time intervals over the On Treatment Period. The summary over the On Treatment Period will include all subjects in the Efficacy Analysis Set. Similar summaries will be provided for the full cohort interval and by 3-month time intervals for each exposure duration cohort.

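### Three seizure variables are defined over the Evaluation Period but analysed through the last BRV dose, so taper days enter them, and SAP 2.5 does not declare the change

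*SAP*

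**What the plan says.** **Defined window.** Protocol 13.1.2.4 lists "Percent reduction in POS (type I) frequency per 28 days from Baseline of the previous study to the Evaluation Period", with POS frequency and seizure freedom over the same period. Protocol 13.1.3.2.2 adds that "the number and percentage of subjects continuously seizure-free during the Evaluation Period will be presented". SAP 2.2.2.2 repeats the definitions, with seizure freedom "for at least 6 months and at least 12 months during the Evaluation Period".

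**Where that window ends.** For discontinued subjects SAP 3.2.4 states: "If the subject enters the Down-Titration Period, then the date of EDV is the end date". Dosing days after the EDV form the Down-Titration Period, which runs to the last dose. For completed subjects SAP 3.2.4 says only that a "subject can potentially have Evaluation Period, Down-Titration Period, or Post-Treatment Period" and gives no end date. Protocol 13.1.3 ends the Evaluation Period at the last Evaluation Visit.

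**Analysed window.** SAP 3.8.1.2 uses diary days "on or after the date of first dose of BRV and prior to or on the date of last dose of BRV". SAP 3.2.1 explains that the last dose may fall in any study period. SAP 3.2.7 says that "the overall duration of exposure (or On Treatment Period) will be calculated as the date of last dose of BRV minus" the first-dose date, plus 1 day. SAP 8.2.1 and 8.2.2 report over this On Treatment Period, and 8.2.3 uses all time on BRV. SAP 8.2.1 adds: "The summary over the On Treatment Period will include all subjects in the Efficacy Analysis Set".

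**Declared changes.** SAP 2.5 mentions only the monotherapy analysis.

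**The concern.** The SAP lists one quantity in section 2.2.2.2 and computes another in section 8.2. The difference is the taper, when the dose is being withdrawn. That is a different condition from individualized maintenance treatment, and the secondary objective is maintenance of efficacy over time. A reader who checks SAP 2.5 for departures from the protocol will not learn of it. For seizure freedom the longer window can turn a run that falls short of 6 or 12 months into a success.

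**Working it through.** The plan gives no figure for this point, and no sample size or power calculation exists. The check compares the windows and then does direct arithmetic.

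**1. Do taper days carry data?** Yes. A Daily Record Card is issued at the EDV (Protocol 11.1.14, 11.2.5), and cards are retrieved and seizures recorded at the Final Visit (11.2.7).

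**2. Who is affected?** Discontinued subjects with an EDV and at least one later dose. Without later dosing, SAP 3.2.4 ends the Evaluation Period at the last dose and the windows coincide. They also coincide for any 3-month interval completed before the EDV. For completed subjects who taper, the overlap cannot be determined, because SAP 3.2.4 gives no end date.

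**3. Shortest taper.** Inputs from Protocol 10.1.1.1: steps of at most 50mg/day per week, with a last week at 20mg/day.
- From 100mg/day: 50, 20 = 2 weeks = 14 days.
- From 150mg/day: 100, 50, 20 = 3 weeks = 21 days.
- From 200mg/day: 150, 100, 50, 20 = 4 weeks = 28 days.

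These are minimum lengths, since smaller steps are allowed.

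**4. Overall seizure freedom.** SAP 8.2.3 accepts any continuous interval. A qualifying run inside the Evaluation Period also lies inside the longer window, and the denominator is the same. The percentage can therefore only rise or stay equal. With required length L and taper D, a run of L - D days up to the EDV can reach L if no seizure is reported in the taper:

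| Taper D | 6 months (L = 180) | 12 months (L = 360) |
|---|---|---|
| 14 days | 166-179 | 346-359 |
| 21 days | 159-179 | 339-359 |

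The 90% diary rule does not prevent this. With otherwise complete diaries, 162/180 = 90%, so any run of at least 162 days passes with no taper entry at all. A run of 159 days gives 159/180 = 88.3% and needs 3 recorded taper days. For 12 months, even 339/360 = 94.2% passes. Each such subject adds 1/108 = 0.93 points, using the 108 enrolled (SAP 2.4), and slightly more if the Efficacy Analysis Set is smaller.

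**5. POS percent reduction.** With R the Evaluation Period reduction, s the taper share of diary days and k the taper seizure rate divided by the Evaluation Period rate, one subject's shift is -(100 - R) × s × (k - 1). The documents give neither R nor k. Assume R = 50%, k from 0.5 to 2, and an EDV at Day 180:
- 14 days: s = 14/194 = 7.2%; shift +1.8 (k = 0.5) to -3.6 (k = 2).
- 21 days: s = 21/201 = 10.4%; shift +2.6 to -5.2.
- k = 1: shift 0.

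If half of all subjects tapered at that time (also assumed), the mean would move by half of this: +0.9 to -1.8, or +1.3 to -2.6. The effect fades with exposure. With a 14-day taper and k = 2, a 50% reduction reads as 43.3% after 90 Evaluation Period days and 48.1% after 360.

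**The case against.** The strongest reply is that the window is deliberate and in plain sight. SAP 3.2.1 says that the last dose need not be in the Evaluation Period. SAP 4.2 bases seizure frequency for early leavers on diary data collected while they were receiving BRV. Protocol 13.3 leaves full analysis details to the SAP. These are other, not secondary, efficacy variables, the study is descriptive, and if seizures rise during the taper the POS summaries are conservative.

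Most of this stands, and it limits the point. A reader might infer a concealed change; SAP 3.2.1, 3.2.7 and 4.2 rule that out. A reader might also infer that the seizure tables are wrong throughout; they are not, because many subjects and intervals have identical windows. What does not fall away is that SAP 2.2.2.2 still lists the Evaluation Period variables, section 8.2 computes something else, and SAP 2.5, whose purpose is to record such differences, is silent.

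A further tempting reading concerns SAP 3.2.5, which admits a subject to a 3-month efficacy interval only if the last dose reaches the interval's last day. Lack or loss of efficacy is a named reason for leaving (Protocol 9.3), so this might look like an error that inflates by-interval reductions. The documents do not support calling it one. The rule is explicit, the overall On Treatment summary keeps every Efficacy Analysis Set subject, and SAP 4.2 addresses dropout through exposure cohorts. The size is unknown, and it is zero if leavers respond like stayers.

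**Conclusion.** The point holds as an undeclared mismatch between the defined and the analysed window for three variables, confined to subjects dosed after the end of their Evaluation Period. It should be corrected, but it does not touch the primary safety objective.

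The direction is certain only for overall seizure freedom: equal or higher, by about 0.9 points for each subject whose run falls in the ranges above. How many such subjects exist cannot be known from the documents. The ranges assume the fastest stated taper; slower tapers widen them, so 14 or 21 days is not a ceiling on taper days.

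A reader might infer that POS reductions are biased in a known direction. They are not: the sign depends on the seizure rate during the taper, which the documents do not give. The POS shifts above rest wholly on assumed inputs, and the mean shift is probably small.

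**What to change.** **Preferred.** In SAP 3.8.1.2 and 8.2.1 to 8.2.3, end the window for the three seizure variables at the end of the Evaluation Period. In SAP 3.2.4, define that end for completed subjects as the last Evaluation Visit, following Protocol 13.1.3. Keep the through-last-dose On Treatment version as supportive, and list it in SAP 2.5.

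**Minimum.** Keep the present analyses, declare the On Treatment window in SAP 2.5, and add Evaluation Period results for overall seizure freedom, POS frequency and percent reduction. The completed-subject end date is still needed.

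**Either way,** state that exposure-cohort and 3-month-interval membership stays based on last dose. A footnote should say that the seizure window can then be shorter than the cohort label: an EDV on Day 76 with a last dose on Day 90 belongs to the cohort of at least 3 months with a 76-day window.

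**Optional, and not part of the error.** Add a by-interval sensitivity table that admits subjects who reach an interval's first day. Partial intervals would be noisier.

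**Cost.** SAP wording and additional seizure tables; no new data. Showing both windows in every overall, interval, cohort and regional table would duplicate a good deal of output, so the supportive version can be limited to the overall summaries.
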